# 9.5.5.1.5 Reporting and Documenting Serious Adverse Events

All SAEs beginning with the time of signing of the ICF and continuing through 4 weeks after the last dose of trial drug must be reported. The following steps will be taken to report promptly and document accurately any SAE, whether or not it appears to be related to trial drug:

Report the SAE to the Sponsor by entering the information into the eCRF immediately and not later than 24 hours after becoming aware that a subject has experienced an SAE. If unable to access the eCRF, the event must be reported by submitting the completed SAE Reporting form immediately and not later than 24 hours after becoming aware that a subject has experienced an SAE (see Section 17.1 for contact information).

After the study is completed at a given site, the electronic data capture (EDC) system will be taken off-line to prevent the entry of new data or changes to existing data.

If a site receives a report of a new SAE from a study subject or receives updated data on a previously reported SAE after the EDC system has been taken off-line, then the site can report this information on the paper-based SAE Reporting Form.

- 2. Perform appropriate diagnostic tests and therapeutic measures and submit all follow-up substantiating data, such as diagnostic test reports, hospital discharge summaries and autopsy report to the Sponsor's representative.
- 3. Conduct appropriate consultation and follow-up evaluation until the SAE outcome is known or the SAE is resolved. Outcomes for reported AEs/SAEs/AESIs are to be defined as follows:
  - Recovering/Resolving
  - Recovered/Resolved
  - Not Recovered/Not Resolved
  - Recovered/Resolved with sequelae
  - Fatal
  - Unknown
- 4. All new information for previously reported SAEs must be sent to the Sponsor **immediately and no later than 24 hours** after Investigator's awareness of the new information. If specifically requested, the investigator may need to provide additional follow-up information, such as discharge summaries, medical records, or extracts

from the medical records. Information provided about the SAE must be consistent with that recorded on the Adverse Events eCRF.

There is no requirement to actively monitor study subjects after the study has ended with regards to study subjects treated by the investigator. However, if the investigator becomes aware of SAEs suspected to be related to investigational product, then these SAEs will be reported to the Sponsor **immediately and no later than 24 hours** after the investigator's awareness of the event. SAEs reported after the end of the study will be captured within the safety database as clinical study cases and handled accordingly based on relationship to investigational product.

If further safety-related data is needed to fulfill any regulatory reporting requirements for a reportable event, then additional information may need to be collected from the subject's records after the subject ends the study.

Review each SAE report and evaluate the relationship of the SAE to trial treatment.

# 9.5.5.1.5.1 Monitoring of Serious Adverse Events Anticipated in the Trial Population

SAEs are anticipated to occur in the trial population independent of the subject's exposure to trial drug. These anticipated SAEs are provided in Section 17.8 (Serious Adverse Events Anticipated in the Trial Population) for reference. The list does NOT change the Investigator's reporting obligations or prevent the need to report an AE meeting the definition of an SAE, as detailed above. The purpose of this list is to alert the Investigator that some events reported as SAEs that are anticipated to occur in the trial population due to underlying disease, may not require expedited reporting to the regulatory authorities in every country/region. The Sponsor will monitor these events throughout the course of the trial for any change in frequency.

# 9.5.5.1.6 Follow-up of Adverse Events

The Investigator is obligated to follow up any reported AE, SAE, or AESI until all relevant clinical data are known to allow for an outcome or the event is resolved, in addition to confirming the causality assessment. Any ongoing trial drug-related AE present at the time of trial termination, including a clinically significant laboratory test abnormality, will be followed until the event is resolved or until the event stabilizes and the overall clinical outcome has been ascertained.

The investigator is obligated to perform or arrange for the conduct of supplemental measurements and/or evaluations as medically indicated or as requested by Sponsor to elucidate the nature and/or causality of the AE or SAE as fully as possible. This may include additional laboratory tests or investigations, histopathological examinations, or consultation with other healthcare professionals.

If a subject is permanently withdrawn from investigational product(s) and/or noninvestigational product(s)/auxiliary medicinal product(s) because of a SAE, this information must be submitted to Sponsor.

The investigator will submit any updated SAE data to Sponsor **immediately and no later than 24 hours** of receipt of the information.

#### 9.5.5.1.7 Medication Errors

A medication error is any unintended failure in the drug treatment process, such as a mistake in the prescribing, dispensing, storing, preparation or administration of a medicine that leads to, or has the potential to lead to harm to the subject.

An overdose is defined as a known deliberate or accidental administration of investigational drug to a subject. For this trial, any dose of fipaxalparant (HZN-825) that is more than the dose that has been assigned will be considered an overdose.

An AE or SAE that is associated with a medication error, such as an overdose, is to be reported according to the procedures outlined in Sections 9.5.5.1.2 and 9.5.5.1.5, respectively. All medication errors or overdoses, with or without an AE or SAE, should be recorded as a protocol deviation and reported to the trial Medical Monitor in a timely manner. AEs or SAEs may not occur immediately after the medication error or overdose.

There is no clinical experience with overdose with fipaxalparant (HZN-825). No specific antidote or detoxification measures can be recommended to date. If accidental overdose is suspected, the subject should be treated symptomatically.

# 9.5.5.1.8 Review of Adverse Events and Emerging New Safety Information

The Sponsor will perform an ongoing review of all AEs and all other emerging new information relevant to the safety of the drug, including periodic review and analyses of cumulative safety data for the trial.

# 9.5.5.1.9 Reporting of Investigational New Drug Safety Reports

The Sponsor will report SAEs associated with fipaxalparant (HZN-825) to the appropriate regulatory authorities and all Investigators in accordance with the local and regional regulatory authorities laws and regulations.

# 9.5.5.1.10 Development Safety Update Reports

The Sponsor will prepare and submit annual safety reports to the FDA. Drug safety update reports will also be submitted to countries and territories as required.

The Sponsor will prepare a single Development Safety Update Report (DSUR) (also referred to as Annual Safety Report in the European Union [EU]) for the Sponsor investigational product. To ensure that consolidated safety information for the study is provided, this single DSUR will also include appropriate information on any other investigational products used in the clinical study, if applicable.

### 9.5.5.1.11 Regulatory Reporting Requirements for Safety Information

If subject is permanently withdrawn from investigational product(s), and/or noninvestigational product(s)/auxiliary medicinal product(s) because of a SAE, this information must be submitted to the Sponsor.

Prompt notification by the investigator to the Sponsor of SAEs is essential so that legal obligations and ethical responsibilities towards the safety of subjects and the safety of a study treatment under clinical investigation are met.

The Sponsor has a legal responsibility to notify both the local regulatory authority and other regulatory agencies about the safety of a study treatment under clinical investigation. The Sponsor will comply with country-specific regulatory requirements relating to safety reporting to the external review body and investigators.

Individual safety reports for suspected unexpected serious adverse reactions will be reported by the Sponsor according to local regulatory requirements (e.g., electronic submission to the Eudravigilance database in the EU as per EU Clinical Trial Regulation 536/2014) as well as Sponsor policy and forwarded to investigators as necessary.

An investigator who receives an individual safety report describing a SAE or other specific safety information (e.g., summary or listing of SAEs) from the Sponsor will file it along with the Investigator's Brochure and will notify the external review body, if appropriate according to local requirements.

For studies in which the treatment assignment is blinded, to comply with worldwide reporting regulations for SAEs, the treatment assignment of subjects who develop serious, unexpected, and related AEs may be unblinded by the Sponsor before submission to regulatory authorities. Aggregate analyses may also be unblinded by the Safety Assessment Team, as appropriate. Investigators will receive notification of related SAEs reports sent to regulatory authorities in accordance with local requirements.

### 9.5.5.1.12 Safety Monitoring Plan

Subject safety will be routinely monitored as defined in the Sponsor's safety surveillance and signal management processes.

### 9.5.5.2 Pregnancy and Lactation Reporting

Pregnancy testing will be performed for WOCBP. Serum pregnancy tests will be analyzed at a central trial laboratory and the urine pregnancy tests will be performed locally. In addition, at-home pregnancy tests will be completed by WOCBP at Weeks 8, 12, 20, 24, 32, 36, 44, and 48 during the Core Phase and at Weeks 60, 64, 72, 76, 84, 88, 96 and 100 during the Extension Phase, and results will be reported to the site.

If a female subject becomes pregnant during the Double-blind Treatment Period, she should immediately notify the Investigator and trial drug dosing should be permanently discontinued but the subject will be asked to continue in the trial for evaluations.

Pregnancy occurring in the partner of a male subject participating in the trial should be reported to the Investigator and the Sponsor immediately upon awareness of pregnancy. Monitoring of the subject's partner should continue until conclusion of the pregnancy.

Subjects should be instructed to continue contraception for 4 weeks after their last dose of trial drug. Pregnancies occurring up to 4 weeks after the last dose of trial drug must also be reported to the Investigator.

Some examples of highly effective contraceptive methods that have a failure rate of <1% per year when used consistently and correctly are:

- Combined (estrogen- and progestogen-containing) hormonal contraception associated with inhibition of ovulation
  - o Oral
  - Intravaginal
  - Transdermal
- Progestogen-only hormonal contraception associated with inhibition of ovulation
  - o Oral
  - o Injectable
  - o Implantable
- Intrauterine device
- Intrauterine hormone-releasing system
- Bilateral tubal ligation
- Vasectomized partner
- Sexual abstinence from heterosexual intercourse

There are no expected drug interactions between fipaxalparant (HZN-825) and hormonal contraceptives.

Abstinence should only be used as a contraceptive method if it is in line with the subject's usual and preferred lifestyle. Periodic abstinence (calendar, symptothermal, postovulation methods) is not an acceptable method of contraception.

Details of all pregnancies and/or lactation in female subjects and pregnancies in female partners of male subjects will be collected after the start of study treatment and until 4 weeks after last dose of trial drug.

If a pregnancy is reported, the investigator is to inform the Sponsor **immediately and no later than 24 hours** of learning of the pregnancy and/or lactation. The Investigator should report pregnancies to the Sponsor by submitting the completed Pregnancy Report Form **immediately** 

Fipaxalparant (HZN-825)
Protocol: HZNP-HZN-825-303
Version 5.0, Amendment 4

and not later than 24 hours after becoming aware that the subject/subject's female partner has become pregnant (see Section 17.1 for contact information). The Investigator should counsel the subject and discuss the possible risks of continuing the pregnancy. If pregnancy continues and the subject signs the pregnancy consent form, monitoring should also continue to the conclusion of the pregnancy and the outcome of the pregnancy should be reported to the Sponsor.

Lactation information will be recorded on the Lactation Notification Form and submitted to Sponsor Global Patient Safety **immediately and no later than 24 hours** of the investigator's awareness of the event.

### 9.5.5.3 Medical History

Medical history, including IPF history and treatment and substance use history, will be recorded.

# 9.5.5.4 Vital Signs, Weight and Height

BP and pulse measurements will be obtained with the subject's arm unconstrained by clothing or other material and while the subject is sitting up. When possible, the same arm will be used for measurements for all trial visits.

Weight and height measurements will be obtained. To limit the potential for variability in weight collection, the subject should wear lightweight clothing and no shoes during weighing.

# 9.5.5.5 Orthostatic Hypotension Assessment

Due to a potential role of LPA in vascular tone (Section 7.1.2), orthostatic hypotension will be assessed at the time points indicated in Section 2.1 and Section 2.2.

BP and heart rate will be measured after the subject has rested ≥5 minutes in the supine position and after 1 minute and 3 minutes in the standing position, as per the Orthostatic Hypotension Assessment Manual provided by the Sponsor. See Section 9.5.5.1.1.4 for more information on orthostatic hypotension assessment.

A copy of the Orthostatic Hypotension Assessment Manual is provided in Section 17.9.

# 9.5.5.6 Physical Examination

A complete physical examination, including but not limited to, cardiac, pulmonary and neurologic assessments, will be performed per the Schedules of Assessments (Section 2.1 and Section 2.2).

# 9.5.5.7 Electrocardiogram

ECG results will be recorded as normal or abnormal on the eCRF and all abnormal results will be evaluated by the Investigator as clinically significant or not clinically significant. Any clinically significant abnormal ECG, including a QT interval corrected for heart rate >450 ms, should be confirmed by a repeat resting ECG at the same visit. The site personnel should ensure that ECGs are collected after the subject is supine for at least 10 minutes.

A copy of the ECG tracing will remain with the source documents

PRIVATE AND CONFIDENTIAL INFORMATION OF HORIZON THERAPEUTICS IRELAND DAC (A WHOLLY OWNED SUBSIDIARY OF AMGEN INC.)

Page 93 of 153

Fipaxalparant (HZN-825) Protocol: HZNP-HZN-825-303 Version 5.0, Amendment 4

# 9.5.5.8 Echocardiogram

A standard transthoracic echocardiogram will be conducted according to the Schedules of Assessments (Section 2.1 and Section 2.2). Echocardiogram results will be recorded on the eCRF as normal or abnormal and all abnormal results will be evaluated by the Investigator as clinically significant or not clinically significant. A copy of the echocardiogram results will remain with the source documents.

# 9.5.5.9 Laboratory Tests for Evaluation

A central trial laboratory will be used for all protocol-specified laboratory evaluations, with the exception of urine pregnancy tests that will be performed locally at each site or at-home, as applicable, in order to maintain monthly pregnancy testing.

Chemistry parameters to be evaluated include total protein, albumin, sodium, phosphate, potassium, calcium, chloride, bicarbonate, blood urea nitrogen, creatinine, creatine kinase, uric acid, glucose, lactate dehydrogenase; liver function tests (ALT, AST, gamma glutamyltransferase, alkaline phosphatase, total bile acid, total bilirubin, conjugated, and unconjugated bilirubin, if applicable).

Fasting glucose and fasting lipid profile (total cholesterol, high-density lipoprotein cholesterol, low-density lipoprotein cholesterol, triglycerides) will also be evaluated (see Sections 2.1 and 2.2).

Hematology parameters to be evaluated include hemoglobin, hematocrit, red blood cell count (with morphology if blood cell count is abnormal), mean corpuscular volume (MCV), mean corpuscular hemoglobin, mean corpuscular hemoglobin concentration, red blood cell distribution width, reticulocyte count, white blood cell count with differential (neutrophils, eosinophils, basophils, monocytes, lymphocytes) and platelet count.

Urinalysis parameters to be evaluated include macroscopic panel (i.e., appearance, bilirubin, blood, color, glucose, ketones, leukocyte esterase, nitrites, pH, protein, specific gravity and urobilinogen) and microscopic panel (i.e., amorphous crystals, bacteria, calcium carbonate crystals, calcium oxalate crystals, calcium phosphate crystals, cysteine crystals, granular casts, hyaline casts, leucine crystals, mucus, red blood cells, renal epithelial cells, squamous epithelial cells, transitional epithelial cells, triple phosphate crystals, tyrosine crystals, uric acid crystals, waxy casts, white blood cells, white blood cell casts and yeast).

Samples for clinical inflammatory laboratory evaluation of high-sensitivity C-reactive protein will also be collected.

The total blood volume for planned visits through the final safety follow-up visit in the Core Phase is approximately 305 mL. Extension Phase, repeat or unscheduled blood tests performed in individual subjects may add to the total blood volume. Instructions for the collection, handling and analysis of clinical laboratory samples will be provided to the site prior to trial site initiation.

# 9.5.6 Appropriateness of Measurements

All safety and efficacy variables, as well as the methods to measure them, are standard variables/methods in clinical trials and/or clinical practice and are widely used and generally recognized as reliable, accurate and relevant.

The L-IPF [Swigris et al., 2020], K-BILD [Patel et al., 2012], LCQ [Birring et al., 2003] and SF-12 [Swigris et al., 2010; Tomioka et al., 2007] have been validated for use in subjects with IPF.

#### 9.5.7 Trial Procedures

Trial procedures and timing are detailed in the Schedules of Assessments (Section 2.1 and Section 2.2).

Visits at Weeks 22, 34 and 46 during the Core Phase and at Weeks 74, 86, and 98 during the Extension Phase may be completed at an alternative remote location, e.g., a subject's home, by a visiting home healthcare professional and will be based on local availability and as allowable based on local laws and regulations. Remote locations will be discussed during the consent process per subject's preference and as approved by the Investigator. Site Investigators will have direct awareness and oversight of remote subject visits.

The end of the trial is defined as the date of the last visit of the last subject undergoing the trial.

#### 9.5.8 Effect of a Pandemic on Trial Procedures

In rare situations due directly to COVID-19 where trial subjects cannot attend scheduled clinic visits, the following modifications may be considered:

- For efficacy assessments, a home visit or a subject-collected FVC may be used. For patient-reported outcomes or other questionnaires, a telephone visit, virtual visit or home visit may be used to collect information.
- For safety assessments, a local laboratory or a home visit may be used to collect laboratory-related assessments to monitor safety and results will be communicated to the Medical Monitor. A telephone visit, virtual visit or home visit may be used to collect information on AEs and drug compliance. Investigators may also consider shipping trial drug to a subject's home via appropriate courier, if necessary.
- If data are captured in an irregular manner (e.g., patient-reported outcomes via telephone or FVC in-home) this should be captured via source documentation. If possible, these protocol modifications should be discussed with the Sponsor and contract research organization prior to implementation, but deviations to immediately address subject safety are possible per the Investigator's discretion.

# 9.6 Statistical Methods and Determination of Sample Size

# 9.6.1 Core Phase

### **9.6.1.1 Endpoints**

# 9.6.1.1.1 Primary Efficacy Endpoint

The primary endpoint is the change in FVC % predicted from Baseline to Week 52.

# 9.6.1.1.2 Key Secondary Efficacy Endpoint

Proportion of subjects with decline in FVC % predicted ≥10% from Baseline at Week 52.

# 9.6.1.1.3 Other Secondary Efficacy Endpoints

- 1. Change from Baseline in the 6MWT results to Week 52.
- 2. Change from Baseline in K-BILD scores to Week 52.
- 3. Change from Baseline in L-IPF scores to Week 52.
- 4. Change from Baseline in LCQ scores to Week 52.
- 5. Time to first hospitalization due to respiratory distress from Baseline up to Week 52.
- 6. Time to first onset of the composite endpoint of PFS from Baseline up to Week 52, where progression includes decline in FVC % predicted ≥10% or death.

# 9.6.1.1.4 Exploratory Endpoints

from Baseline up to Week 52.	

# 9.6.1.1.5 Safety and Tolerability Endpoints

- 1. Incidence of TEAEs, SAEs and the AESI (orthostatic hypotension).
- 2. Concomitant medication use.
- 3. Vital signs.
- 4. 12-lead ECGs and echocardiograms.
- 5. Laboratory evaluations.

# 9.6.1.1.6 Pharmacokinetic Endpoint

1. Pre- and post-dose concentrations of fipaxalparant (HZN-825).

### 9.6.1.2 Analysis Sets

Three analysis sets will be defined for the Core Phase of the trial. The full analysis set (FAS) will include all subjects who are randomized to treatment and take at least 1 dose of trial drug. This will be the analysis set used for efficacy data analyses and subjects will be analyzed according to the treatment to which they were randomized. The safety analysis set will include all subjects who receive at least 1 dose or partial dose of trial drug. The PK analysis set will include all subjects who receive at least 1 dose or partial dose of fipaxalparant (HZN-825) and have at least 1 PK sample post fipaxalparant (HZN-825) treatment.

# 9.6.1.3 Primary Efficacy Endpoint Analysis

The estimand for the primary efficacy analyses will be constructed to compare the primary endpoint between each dose regimen of fipaxalparant (HZN-825) and placebo using the treatment policy strategy approach to intercurrent events. All subjects who are randomized and take at least 1 dose of trial drug will be included in the primary efficacy analyses (FAS).

The primary efficacy endpoint will be change from Baseline in FVC % predicted to Week 52. A mixed model for repeated measures (MMRM) analysis of covariance model will be fit to the data using observed change in FVC % predicted values from all planned post-Baseline assessments (i.e., Weeks 4, 16, 28, 40, and 52) with covariates of stratification factors (concomitant use of IPF therapy [yes, no] and FVC % predicted at Baseline [≥70%, <70%]), treatment group, visit and visit-by-treatment group interaction. The unstructured variance-covariance matrix will be used in the model. Treatment group least squares means, associated standard error (SE) and their differences (each fipaxalparant [HZN-825] group minus placebo separately), SE of the difference, 90% CIs and p-value overall and for each visit will be provided.

For subjects with missing data at 1 or more time points, the available data will be included in the analysis.

As a supplemental analysis to assess the robustness of the efficacy analysis results, the effect of each dose regimen of fipaxalparant (HZN-825) will be compared to placebo using the following measurements and methods:

Horizon Therapeutics Ireland DAC (a wholly owned subsidiary of Amgen Inc.) Date: 07 October 2024

IND 154671

Fipaxalparant (HZN-825) Protocol: HZNP-HZN-825-303 Version 5.0, Amendment 4

- Change in FVC (in mL) from Baseline to Week 52 using a similar MMRM analysis method as described for the primary efficacy endpoint
- Cumulative response curve comparison using the Kolmogorov-Smirnov test on:
  - The range of improvement (≥0% to ≥15% with a 5% increment) and worsening (< -15% to <0% with a 5% increment) based on the change in FVC % predicted value from Baseline at Week 52

  - The range cut-off values from less than -300 mL to greater 100 mL with a 100-mL increment based on the change in FVC (in mL) from Baseline at Week 52

One sensitivity analysis will consider whether data missing not at random may change the conclusion. A tipping point analysis will estimate the difference in true values among unobserved data that must occur to change the conclusion for each dose (i.e., change the result for each dose from  $p \le 0.10$  to p > 0.10).

Potential intercurrent events such as discontinuing from the treatment, early discontinuing from the trial, initiating rescue therapy, death, lung transplant or potentially COVID-19, may occur during the trial. Intercurrent events will be addressed in the primary analysis by using treatment policy strategy with all available data. Supplemental analyses will assess the use of rescue medication. The proportion of subjects who qualify for and who receive rescue medication at each potential time point will be summarized for each treatment group to determine whether there are different use rates between treatment groups. A supplemental analysis will repeat the primary analysis except that it will ignore all FVC data collected after the initiation of rescue medication; the result will be a sensitivity analysis that uses a hypothetical strategy approach to the intercurrent even of initiation of rescue medication. A detailed plan for sensitivity/ supplemental analyses regarding potential intercurrent events including how to handle the data impacted by COVID19, will be provided in the statistical analysis plan.

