# 9.6.3 Sample Size and Power Considerations

Approximately 135 subjects (45 subjects per treatment group) will be enrolled in the trial. Based on a prior trial of pirfenidone [Nathan et al., 2019] in a similar subject population, change in FVC % predicted is expected to have a standard deviation of 6% to 9% after 52 weeks of treatment. Assuming a clinically important difference between fipaxalparant (HZN-825) and placebo is 3% and a common standard deviation is 9%, a sample size of 45 subjects per treatment group in the Core Phase will provide 85% probability to detect a positive signal (FVC % predicted difference for each dose vs. placebo at Week 52 >1%) and 70% probability to detect a positive signal (FVC % predicted difference for each dose vs. placebo at Week 52 >2%). If the true FVC % predicted difference for each dose versus placebo at Week 52 is 0%, then there is only 15% probability to detect a positive signal (FVC % predicted difference for each dose vs. placebo at Week 52 >2%).

The sample size for the Extension Phase is based on the number of subjects who complete the Core Phase.

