2.5. Changes from the Protocol Planned Analyses

The definition of HZN-825 Baseline has been updated from the protocol. This adjustment is essential to facilitate a comprehensive comparison of data over 104 weeks across all cohorts. As a result, HZN-825 Baseline has been redefined as the latest measurement prior to the first dose of study drug (either HZN-825 or Placebo) during the Core Phase.

For efficacy analysis, the prior use of IPF approved therapy will be used as a covariate in the mixed model for repeated measures instead of concomitant use of IPF approved therapy. In earlier protocol versions, the prior use of IPF approved therapy was used as a stratification factor, while concomitant use of IPF approved therapy was restricted. In protocol version 4, concomitant use of IPF approved therapy was permitted and used as a stratification factor. However, only a small number of enrolled subjects were on concomitant IPF therapy. To ensure a robust model estimate, the prior use of IPF approved therapy will be used in the model. Additional subgroup analysis will be conducted as needed, focusing on subjects who were on concomitant use of IPF approved therapy.

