6. EFFICACY ANALYSES

6.1. Core Phase

6.1.1. Primary Efficacy Endpoint

6.1.1.1. Primary Analysis Method

The primary efficacy endpoint is the change from Baseline in FVC % predicted at Week 52. The FVC% predicted data are collected at Screening, Day 1, Week 4, Week 16, Week 28, Week 40, and Week 52.

The estimand for the primary efficacy analyses is constructed to compare the primary endpoint between each dose regimen of HZN-825 and placebo, using the treatment policy strategy approach to ICEs without data imputation in FAS subjects.

The primary analysis will be based on a mixed model for repeated measures (MMRM) analysis of covariance (ANCOVA) model using observed change in FVC % predicted values from all planned post-baseline assessments (Weeks 4, 16, 28, 40 and 52) with covariates of treatment group (300 mg HZN-825 QD, 300 mg HZN-825 BID, placebo), prior use of IPF therapy [yes or no], FVC% predicted at baseline [≥ 70, <70], visit week, and treatment by visit week interaction. An unstructured covariance matrix will be used as the primary analysis method; if the model does not converge, the following three variance-covariance matrices or by visit week will be attempted in order until one converges: heterogeneous Toeplitz (TOEPH), heterogeneous compound symmetry (CSH), and Toeplitz (TOEP).

Treatment group least squares means, associated standard error (SE) and their differences (each HZN-825 group minus placebo separately), SE of the difference, 90% CIs and p-values for each visit will be provided with Week 52 estimands being the primary efficacy endpoint result. A line plot of the LS mean value for FVC% predicted change from Baseline will be plotted by treatment group for each visit week over time, including the estimated 90% CI around each LS mean.

Change in FVC % predicted will also be summarized descriptively for observed cases at each visit.

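### The primary MMRM has no stratum-by-visit terms; if stratum effects grow over time, the Week 52 standard error is modestly larger than it needs to be

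*Protocol*

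**What the plan says.** Protocol 9.6.1.3 fits change in FVC % predicted at "all planned post-Baseline assessments (i.e., Weeks 4, 16, 28, 40, and 52". The covariates are the IPF-therapy factor and then "FVC % predicted at Baseline [≥70%, <70%]), treatment group, visit and visit-by-treatment group interaction". On the covariance it says "The unstructured variance-covariance matrix will be used in the model".

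SAP 6.1.1.1 keeps this structure, with prior IPF therapy followed by "FVC% predicted at baseline [≥ 70, <70], visit week, and treatment by visit week interaction". SAP 2.5 explains the swap of therapy factor: "the prior use of IPF approved therapy will be used as a covariate in the mixed model for repeated measures instead of concomitant use". SAP 5.2 records that prior use was a randomisation factor only before Protocol Version 4.0.

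Neither document crosses a stratification factor with visit. Amendment 3 removed continuous baseline FVC % predicted from the models, so these two binary factors are the only baseline adjustment. The Week 52 contrast is the primary result.

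**The concern.** A main effect in this model is one number shared by all five visits. The outcome is change from Baseline, so an effect of severity or treatment history on the rate of decline would start near zero and widen. Generalised least squares gives most weight to the visits with the least variance, which are then the early ones. The shared coefficient settles near the small early effect, and much of the Week 52 stratum effect stays in the Week 52 residual.

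At stake is precision in the test that opens the hierarchy. BID against placebo on the primary endpoint gates QD and the key secondary endpoint. On the plan's own inputs that test has about 47.5% power for a 3-point difference, so an avoidable loss is worth removing if the remedy is cheap.

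**Working it through.** **The plan's own figures.** Protocol 9.6.3 gives "Approximately 135 subjects (45 subjects per treatment group) will be enrolled in the trial", "a common standard deviation is 9" percent, and "clinically important difference between fipaxalparant (HZN-825) and placebo is 3" percent.
- SE = 9 × √(2/45) = 1.897.
- Φ((3−1)/1.897) = 85.4%, Φ((3−2)/1.897) = 70.1% and 1−Φ(2/1.897) = 14.6%. These reproduce the stated 85%, 70% and 15%.
- Power of the two-sided 0.10 test at 3 points, which the plan does not state: Φ(3/1.897 − 1.645) + Φ(−3/1.897 − 1.645) = 47.5%.

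**Assumptions.** The documents give no stratum effect, time course, visit-specific SD or correlation. I assume:
- a random slope plus reading error with SD e of 1.5 or 3 at Baseline and at each visit;
- stratum effects growing linearly from zero;
- a 50/50 split on each factor, with the factors uncorrelated;
- complete data, and total Week 52 SD held at 9.

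The visits are those of SAP 6.1.1.1; Table 2 in SAP 6.1.1.2 lists them without Week 4.

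**Step 1: share of the Week 52 effect captured.** For an effect with time profile g, the shared coefficient tends to the fraction f = (1'S⁻¹g)/(1'S⁻¹1) of its Week 52 value. Take g = t = (4, 16, 28, 40, 52)/52 and S = D·tt' + e²(I + 11'), with D = 81 − 2e². Write r = D/e². The sum of t is 2.692, its square is 7.249, and the sum of t² is 1.982. Then f = [2.692/(1 + 1.982r)] ÷ [5 − 7.249r/(1 + 1.982r)].
- e = 3: D = 63, r = 7, f = 0.181/1.589 = 0.114.
- e = 1.5: D = 76.5, r = 34, f = 0.0394/1.397 = 0.028.

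So about 3% to 11% is captured. Taking the stratum variance out of the slope variance moves the upper figure to about 13%. With 36 in place of 81 (SD 6, the low end of the plan's range) the range is 6% to 26%.

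**Step 2: effect on the SE.** For k factors each worth d points at Week 52, the within-stratum variance is w = 81 − k·d²/4. The stratum variance left in the residual is u = k·((1−f)d)²/4. The SE ratio is √(1 + u/w), with SEs √((w+u)·2/45) and √(w·2/45). Example with k = 1, d = 4, f = 0.114: w = 77, u = 3.14, ratio 1.020. Each range below runs from e = 3 to e = 1.5.

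| Factors × points | SE excess | SE as planned | SE with interactions | Power for 3 points |
|---|---|---|---|---|
| 1 × 2 | 0.5–0.6% | 1.895–1.897 | 1.886 | 47.6–47.5% → 47.9% |
| 1 × 4 | 2.0–2.4% | 1.887–1.895 | 1.850 | 47.9–47.6% → 49.1% |
| 2 × 3 | 2.3–2.7% | 1.886–1.894 | 1.844 | 47.9–47.6% → 49.3% |
| 2 × 4 | 4.2–5.0% | 1.877–1.892 | 1.801 | 48.2–47.7% → 50.9% |

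**Step 3: other assumptions, one factor worth 4 points.**
- Square-root time course, e = 3: 36% captured, SE excess 1.05% instead of 2.02%.
- Other covariance shapes with variance growing over time, linear effect: −10% to 18% captured, excess 1.8% to 3.1%. In the worst of these a square-root course gives 2.1% against 3.1%.
- Constant variance with equal correlation, linear effect: the share is the mean of t, 28/52 = 54%, and the excess is 0.55%.
- A 20/80 split, linear effect, e = 3: 1.27%.
- Flat effect: 100% captured, no excess.

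**Step 4: bias and level.** Simulated trials with two strata and an assumed 20% dropout (60 per scenario) gave SE ratios of 1.008–1.013 for 2 points each and 1.033–1.057 for 4 points each. Mean treatment estimates from the two models agreed within 0.02 points. For a 4-point FVC category balanced by the stratified randomisation, the nominal 0.10 test runs at 2 × (1 − Φ(1.645 × 1.020)) = 0.093.

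**The case against.** A reader might infer that the stratification factors are practically unadjusted at Week 52 and that the reported SE is overstated as a matter of fact. The documents do not support that. Both statements need a stratum effect that widens and an outcome variance that grows. Across reasonable assumptions the share captured runs from about none to all of the effect.

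The size can also be questioned. A factor worth 3 or 4 points matches or exceeds the 3-point treatment difference the trial was planned around. The sample-size probabilities reproduce with the unadjusted SE, so the design relies on no covariate gain.

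Nor does the argument apply equally to both covariates. The claim that stratified randomisation has already reduced the true variance, so that the test is conservative, holds for the FVC category. Prior therapy was a randomisation factor only before Version 4.0. For subjects randomised later, weak adjustment for it costs precision but does not make the SE wrong.

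Finally, SAP 6.1.1.3 already plans a rank ANCOVA on Week 52 with the same covariates, though only as a sensitivity analysis.

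All of this stands. It makes the point conditional and small. It does not supply the missing interactions.

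**Conclusion.** The specification is clear: one coefficient per baseline factor across Weeks 4 to 52, in both documents. If stratum effects and variance both grow over time, the primary SE at Week 52 is modestly larger than it need be, by the amounts in the table. All of those figures rest on the listed assumptions rather than on the documents.

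A reader might also suspect bias in the treatment estimate or an inflated type I error. Neither follows, because treatment is crossed with visit and allocation is randomised. Any error is in the conservative direction for the FVC category and is mainly lost precision for prior therapy. This is a cheap improvement of low severity, not an error that threatens the primary conclusion.

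**What to change.** In protocol 9.6.1.3 and SAP 6.1.1.1, add baseline-FVC-category-by-visit and IPF-therapy-by-visit interactions to the primary MMRM, using whichever therapy factor is kept. Carry the same terms into the fallback covariance fits. Blinded staff should decide this before Core Phase unblinding.

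Extending the terms to the MMRMs for 6MWT, K-BILD, L-IPF and LCQ is optional, for consistency. Those endpoints have no Week 4 assessment, so the pull toward the earliest visit is less of an issue there.

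The cost is one line of text and code, and eight more fixed-effect parameters (2 factors × 4 additional visits) with about 135 subjects. The estimand does not change and no new data are needed. In a simulated check with no gain to be had, the extra terms raised the SE by only about 0.2%.
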